5.2.2. Sponsor-Defined Outcome of *S. aureus* Pneumonia

Sponsor-Defined Outcome (SDO) of *S. aureus* pneumonia will be determined programmatically based on the data and the manual review conducted at Review Meetings per the POP.

Each randomized subject will be evaluated for the occurrence of *S. aureus* pneumonia between Randomization and up to, but not including, Day 22. In order to assign a SDO, the following assessments will be made based on available data:

1. Microbiological Assessment
2. Chest Imaging Assessment
3. Clinical Assessments
 - a. Respiratory
 - b. Signs and Symptoms
4. Operational Assessments

There will be 2 SDO definitions for data analysis: SDO1 and SDO2. The 2 definitions will need to satisfy the 4 assessments above and differ only on the clinical assessments. SDO1 will meet either respiratory OR signs and symptoms requirements while SDO2 will meet both respiratory AND signs and symptoms requirements.

The individual assessments for each randomized subject will be collapsed to assign an SDO1/SDO2 of Yes, No, Indeterminate (i.e. insufficient data to assign a SDO of Yes or No), or Censored (i.e. subject died prior to the Day 22 assessment) based on the mutually exclusive, hierarchical rules specified in the POP.

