6. SAMPLE SIZE DETERMINATION

The estimated incidence of progression to *S. aureus* pneumonia in mechanically ventilated subjects with heavy endotracheal colonization of *S. aureus* is approximately 25% within 22 days of randomization.

Assuming a 2-sided significance level of 0.05 and a desired power of 80% to detect a significant difference between *S. aureus* pneumonia incidence rates of 25% in the placebo group and 12.5% in the ASN100 treatment group (50% reduction), 152 evaluable subjects are required in each treatment group. A sample size of 304 subjects (152 subjects per treatment group) will yield 80% power to detect a 50% reduction in the incidence of *S. aureus* pneumonia with ASN100 treatment when assuming a 25% incidence rate of *S. aureus* pneumonia in placebo-treated subjects. Assuming a 14% non-evaluable rate, approximately 354 subjects (177 subjects per treatment group) will be randomized. Assuming the screen failure rate is about 84%, approximately 2250 subjects will be screened.

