7.11.1. Primary Efficacy Endpoint

The primary efficacy endpoint is whether the subject has or has not developed *S. aureus* pneumonia up to, but not including, Day 22 in the MITT Population. For the primary analysis, whether the subject has or has not developed *S. aureus* pneumonia will be based on sponsor defined outcome (SDO1).

The primary analysis is based on comparing two proportions of subjects who develop *S. aureus* pneumonia by SDO1 up to, but not including, Day 22. For each arm, the empirical proportion is defined by a ratio, which is the number of *S. aureus* pneumonia events divided by the total number of subjects in the arm. The inference about the difference of two population rates is based on the empirical counterpart. Specifically, the point estimate, 95% confidence interval and p-value for the rate difference. If subjects discontinued from the study due to any cause prior to Day 22, it will be considered as not developing *S. aureus* pneumonia by SDO1 for the primary efficacy analysis.

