- The Kaplan-Meier analysis will be performed for the proportion of subjects who develop *S. aureus* pneumonia up to but not including Day 22 as determined by SDO1 and the Review Meeting's determination of *S. aureus* as a causative pneumonia pathogen.
- The Kaplan-Meier analysis will be performed for the proportion of subjects who develop *S. aureus* pneumonia up to but not including Day 22 as determined by SDO2 and the Review Meeting's determination of *S. aureus* as a causative pneumonia pathogen
- The Kaplan-Meier analysis will be performed for the proportion of subjects who develop *S. aureus* pneumonia up to but not including Day 22 as determined by the Investigator's judgement and the Review Meeting's determination of *S. aureus* as a causative pneumonia pathogen.
- An additional Kaplan-Meier analysis will be conducted for subjects with *S. aureus* pneumonia and presumed *S. aureus* pneumonia by SDO1 and SDO2. The presumed *S. aureus* pneumonia population includes those subjects with microbiologic results "Not Done" up to and including Day 7 (presumed *S. aureus* pneumonia).
- A third Kaplan-Meier analysis will be conducted for subjects with *S. aureus* pneumonia including those subjects with microbiologic results "Not Done" up to and including Day 10 (presumed *S. aureus* pneumonia) for both SDO1 and SDO2 populations.
- The proportion of subjects who develop *S. aureus* pneumonia up to but not including Day 22 as determined by the Investigator's judgement and the Review Meeting's determination of *S. aureus* as a causative pneumonia pathogen will be obtained from Kaplan-Meier estimates for each treatment group. Discontinuation from the study due to any cause up to but not including Day 22 will be considered as an 'Event'.
- The proportion of subjects who develop *S. aureus* pneumonia up to but not including Day 22 as determined by the Investigator's judgement and the Review Meeting's determination of *S. aureus* as a causative pneumonia pathogen will be

- obtained from Kaplan-Meier estimates for each treatment group incorporating censoring. Discontinuation from the study due to any cause up to but not including Day 22 will be considered censored.

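### Subjects with an Indeterminate SDO1 count as non-events in the primary proportion, and the planned worst-case proportion analysis leaves them there unless they discontinued

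*SAP*

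**What the plan says.** - **Outcome.** SAP 5.2.2 assigns each randomized subject an SDO1 and SDO2 of Yes, No, Indeterminate or Censored. Indeterminate is its own category: "Indeterminate (i.e. insufficient data to assign a SDO of Yes or No". The assignment rules are in the Population and Outcome Plan (POP), which is not among the documents.
- **Primary proportion.** SAP 7.11.1 defines it, per arm, as the number of "pneumonia events divided by the total number of subjects in the arm". The only missing-outcome rule stated for it (7.3.2 and 7.11.1) is that discontinuation before Day 22 is a non-event.
- **Worst-case proportion.** The second bullet of 7.11.2 repeats the comparison with discontinuations scored as events. It does not mention Indeterminate.
- **Kaplan-Meier analyses.** SAP 7.3.2 censors Indeterminate subjects unless otherwise noted. Two further analyses in 7.11.2 add subjects whose microbiology was *Not Done* as presumed *S. aureus* pneumonia, one through Day 7 and one "up to and including Day 10".
- **Reporting.** The end of 7.11.2 tabulates Indeterminate counts by arm.
- **Sample size.** SAP 6 states that "152 evaluable subjects are required in each treatment group", and then: "Assuming a 14% non-evaluable rate, approximately 354 subjects (177 subjects per treatment group) will be randomized".

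**The concern.** The plan recognises that some subjects will lack the data to be called Yes or No, yet the primary ratio has room only for events and everyone else. No sentence says that Indeterminate means No; it follows from the ratio. A subject who stays in the study to Day 22 with an Indeterminate outcome is then a non-event in the primary analysis and again in the analysis meant to test the opposite assumption.

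Some missing microbiology is foreseeable. Respiratory specimens after randomization are collected only when clinically indicated (SAP 5.2.1), and for intubated subjects the protocol accepts only lavage or protected-brush specimens (Protocol 7.4.1). At stake is whether a significant primary result could depend on how a handful of undetermined subjects were scored, with no planned analysis to show it.

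**Working it through.** **Inputs.** From SAP 6: two-sided alpha 0.05, 80% power, 25% against 12.5%, 152 evaluable and 177 randomized per arm, 14% non-evaluable. The Indeterminate rate u is not in the documents. I assume up to 14%; the top of that range is the entire non-evaluable allowance, used only as a ceiling.

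**1. The plan's own figure.** n = [1.96·√(2·p̄·(1−p̄)) + 0.8416·√(p1(1−p1)+p2(1−p2))]² / (p1−p2)², with p̄ = 0.1875:
- (1.0819 + 0.4586)² / 0.125² = 2.373 / 0.015625 = 151.9, so 152 per arm.
- 152 / 0.86 = 176.7, so 177 per arm, 354 in all. Both figures reproduce.

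**2. Equal Indeterminate rates.** Scored as non-events, each rate becomes p(1−u). Scored as events, it becomes p(1−u)+u. Power = Φ{[d − 1.96·√(2·p̄(1−p̄)/n)] / √[(p1(1−p1)+p2(1−p2))/n]}, where d = p1−p2.

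| Assumed u | Rates if non-events | Difference | Power, 177 per arm | Power, 152 per arm | Power if events, 177 per arm |
|---|---|---|---|---|---|
| 0% | 25% vs 12.5% | 12.5 | 85.7% | 80.0% | 85.7% |
| 5% | 23.75% vs 11.88% | 11.88 | 83.4% | 77.5% | 76.1% |
| 10% | 22.5% vs 11.25% | 11.25 | 80.9% | 74.7% | 66.7% |
| 14% | 21.5% vs 10.75% | 10.75 | 78.8% | 72.4% | 59.7% |

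Worked line for 14%, non-events, n = 177: (0.1075 − 0.0766) / 0.0387 = 0.80, and Φ(0.80) ≈ 78.8%. The 177 column assumes every randomized subject reaches the MITT Population. The 152 column applies if the 14% is lost before that.

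**3. Unequal Indeterminate rates, no true effect.** True risk 25% in both arms, also among Indeterminate subjects; 5% Indeterminate on placebo, 15% on ASN100:
- Observed rates: 0.25×0.95 = 23.75% and 0.25×0.85 = 21.25%, a spurious benefit of 2.5 points.
- Chance of a significant result favouring ASN100 at 177 per arm: 1 − Φ[(0.0870 − 0.0250)/0.0444] = 8.1%, against a nominal 2.5%.
- A smaller imbalance, 5% against 10%, shifts the difference by 0.25×5 = 1.25 points and gives 4.6%. If every Indeterminate subject were a true case, the shift would be the full 5 points; that is an extreme, not an expectation.

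**4. Fragility (illustrative counts, Wald interval).**
- 38/177 against 19/177: difference 10.7 points, 95% CI 3.2 to 18.3, p = 0.0055.
- Six ASN100 subjects (3.4% of the arm) re-scored as events, 38/177 against 25/177: 7.3 points, CI −0.6 to 15.3, p = 0.07.
- Twelve re-scored in each arm: the difference is unchanged and p = 0.015.

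A worst case applied equally to both arms can therefore leave the result significant when a one-sided shift would not. That is why a by-arm analysis is needed as well.

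**The case against.** A reader might infer that missing diagnostic data is always scored as success and that nothing planned would reveal it. The documents do not support that.
- Indeterminate subjects are censored, not counted as No, in the Kaplan-Meier SDO1 analysis, which gives a between-arm difference with an interval and p-value.
- The Day 7 and Day 10 analyses turn some missing microbiology into events.
- Indeterminate counts by arm would expose an imbalance.
- HABP and VABP, defined in 5.2.1 without a culture requirement, are reported by arm up to Day 22 (7.11.4).
- The Per Protocol repeat requires adequate monitoring assessments and may drop some data-poor subjects.
- An Indeterminate subject who also discontinued is already re-scored in the worst case.
- A central laboratory result can stand in where the local culture was not done, was improper or showed no growth (5.2.1), which limits the category.

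All of this stands. What remains is that censoring assumes these subjects resemble those still at risk, the *Not Done* analyses stop at Day 10 and do not address missing imaging or clinical data, HABP and VABP are descriptive and not specific to *S. aureus*, and a table of counts is not a bound.

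Three other inferences also go too far. SAP 6 does not define non-evaluable as Indeterminate; the 14% may be subjects lost between randomization and MITT, so no contradiction with the sample size is shown. Without the POP, nothing shows that Indeterminate subjects are enriched for true pneumonia. Nor is the direction known: the trial is double-blind, and if the drug works and these subjects are mostly unproven cases, they would fall more on placebo and the scoring would be conservative.

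**Conclusion.** The point holds in a limited form. Indeterminate subjects who remain in the study are non-events in both the primary and the worst-case proportion, and no planned analysis bounds the primary result for all of them. This is a gap in sensitivity analysis, not evidence that the primary result is biased.

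Its size cannot be fixed from the documents. Equal rates cost little: power falls from 85.7% with none Indeterminate to 78.8% at the 14% ceiling, with 177 per arm. The material risk is imbalance, of the order of 2.5 points and an 8% one-directional error for a 10-point imbalance at 25% risk. Those figures rest on assumed Indeterminate rates, on the planning event rates, and on the scoring that the 7.11.1 ratio implies. If the POP holds a different rule, the SAP should state it.

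**What to change.** 1. In 7.11.1, state that an Indeterminate SDO1 counts as a non-event in the primary proportion.
2. In the second bullet of 7.11.2, count Indeterminate SDO1/SDO2 as events together with discontinuations.
3. Add a tipping-point analysis that varies, separately by arm, how many Indeterminate subjects are scored as events, and report where the conclusion changes.

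Lengthening the *Not Done* presumption to Day 21 is a matter of preference; the documents do not show the Day 7 and Day 10 limits to be wrong.

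Cost: a few lines of SAP text and a few more sensitivity tables, with no new data. SAP 3 allows modification before unblinding. The extended worst case has only about 60% power at an assumed 14% Indeterminate, so it should be labelled a bound and not read as a competing estimate.

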5.2.3. Pharmacokinetic Assessments

Blood samples will be obtained for the measurement of ASN-1 and ASN-2 in serum. Blood samples for PK analysis will be collected immediately following the completion of the second infusion (+15 minutes) and at 6 hours (± 4 hours) and 24 hours (± 6 hours) post-dose following the second infusion. In addition, a PK sample will be obtained from all subjects on Days 4 (± 1 day), 7 (± 1 day), 14 (± 2 days), and 22 (+2 days) of the Monitoring Period. Additional PK samples will be collected on the day of discharge (if discharge occurs between Day 40 and Day 90), on Day 90 (if hospitalized or if the subject is able to return to the clinic), or Early Termination (if applicable).

Select sites will be invited to participate in a BAL fluid PK sub-study. Approximately 25 to 35 subjects who volunteer will participate in this sub-study and will have BAL fluid collected 48 hours (± 36 hours) post-dose (on approximately Day 2 or Day 3, depending on time of study drug administration) to determine ASN-1 and ASN-2 levels and blood to ELF ratio. Subjects participating in the BAL fluid PK sub-study will have a blood sample collected for PK measurement ± 1 hour relative to BAL fluid collection.

If BAL fluid is collected as part of a standard of care procedure from any subject enrolled in the sub-study at any other time post-randomization for any other reason, if possible, a sample for PK analysis will also be obtained. Additionally, attempts will be made to collect a serum sample for PK measurement ± 1 hour relative to BAL fluid collection.

5.2.4. Primary Efficacy Endpoint

The primary efficacy endpoint is whether the subject has developed an SDO1 of *S. aureus* pneumonia up to, but not including, Day 22. The summary measure for efficacy is the proportion of subjects in the MITT Population who develop an SDO1 of *S. aureus* pneumonia up to, but not including, Day 22.

Analyses of the primary efficacy endpoint will also be performed separately for the ITT and PP Populations.

5.2.5. Secondary Efficacy Endpoints

The secondary efficacy endpoints are:

- Duration of mechanical ventilation during the first 21 days post-randomization for subjects in the MITT, ITT, and PP Populations;
- Length of ICU stay during the first 21 days post-randomization for subjects in the MITT, ITT, and PP Populations;
- The C_{max} , T_{max} , AUC, and $t_{1/2}$ of ASN-1 and ASN-2 in serum following a single dose of ASN100 in the PK Population; and
- 28-day all-cause mortality in the MITT, ITT, and PP Population.

5.2.6. Exploratory Efficacy Endpoints

Exploratory efficacy endpoints include:

- Proportion of subjects in the MITT and PP Populations with a diagnosis of HABP >48 hours post-extubation up to, but not including, Day 22 in extubated subjects;
- Proportion of subjects in the MITT and PP Populations with development of VABP up to, but not including, Day 22;
- Incidence of all bacterial pneumonias in the MITT, ITT, and PP Populations;
- Incidence of other non-*S. aureus* bacterial pneumonias up to, but not including, Day 22 in the MITT, ITT, and PP Populations; and
- Incidence of other *S. aureus* infections acquired up to, but not including, Day 22 in the MITT, ITT, and PP Populations.

5.2.7. Safety Endpoints

Safety endpoints are as follows:

1. Treatment-emergent adverse events (TEAEs)
2. Vital signs
3. Electrocardiograms (ECGs)
4. Laboratory parameters
5. Physical examinations

6. Radiographs and Imaging
7. Immunogenicity and anti-drug antibodies

6. SAMPLE SIZE DETERMINATION

The estimated incidence of progression to *S. aureus* pneumonia in mechanically ventilated subjects with heavy endotracheal colonization of *S. aureus* is approximately 25% within 22 days of randomization.

Assuming a 2-sided significance level of 0.05 and a desired power of 80% to detect a significant difference between *S. aureus* pneumonia incidence rates of 25% in the placebo group and 12.5% in the ASN100 treatment group (50% reduction), 152 evaluable subjects are required in each treatment group. A sample size of 304 subjects (152 subjects per treatment group) will yield 80% power to detect a 50% reduction in the incidence of *S. aureus* pneumonia with ASN100 treatment when assuming a 25% incidence rate of *S. aureus* pneumonia in placebo-treated subjects. Assuming a 14% non-evaluable rate, approximately 354 subjects (177 subjects per treatment group) will be randomized. Assuming the screen failure rate is about 84%, approximately 2250 subjects will be screened.

7. STATISTICAL ANALYSIS

7.1. General Statistical Considerations

Summary statistics will be presented by treatment group. For continuous variables, the number of observations (n), mean, standard deviation (SD), median, minimum, and maximum will be provided. For categorical variables, the frequency and percentage in each category will be displayed.

For summary statistics, the mean and median will be displayed to one decimal place greater than the original value and the measure of variability (e.g., standard deviation) will be displayed to two decimal places greater than the original value.

All statistical tests will be performed at the 0.05 significance level using 2-sided tests, except where otherwise noted. All confidence intervals will have a confidence level of 95%.

7.2. Treatment Misallocations

If subjects were randomized but were not treated, the subjects will be included in the ITT Population, but not included in the MITT, PP, PK, and Safety Populations consistent with their definitions.

If subjects were randomized but received incorrect study medication, they will be reported under their randomized treatment group for all efficacy analyses for the ITT, MITT, and PP Populations, but will be reported under the treatment they actually received for all safety analyses for the Safety Population.

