Semi-quantitative cultures using chromogenic media are preferred for determination of eligibility for randomization; however, any quantitative or semi-quantitative culture performed that indicates that a subject is heavily colonized with *S. aureus* is permitted if the culture results are available to randomize the subject within 48 hours (or up to 60 hours with Medical Monitor approval) from the time the ETA specimen was collected.

Once an enrolled subject has an ETA culture reported positive for heavy *S. aureus* colonization and meets all of the inclusion and none of the exclusion criteria, they are eligible for randomization. If they are not randomized on this occasion according to the protocol, they are no longer eligible for continued ETA sampling or randomization, and will be discontinued from the study; however, if subjects are extubated and subsequently re-intubated/mechanically ventilated, they are eligible for re-screening as a new subject enrollment, provided all entry criteria continue to be met. Subjects who were previously randomized are not eligible to be re-consented and re-screened.

At the time of randomization, if a subject's screening ETA culture also shows heavy colonization of a Gram-negative organism (i.e. heavy co-colonization of both Gram-positive and Gram-negative organisms), the subject will not be randomized into the study; however, randomization should not be delayed while waiting for Gram-negative results if heavy colonization with *S. aureus* has been confirmed. Testing for Gram-negative colonization is however not a requirement of the study protocol and would apply to centers that routinely test for both Gram-positive and Gram-negative organisms as part of standard of care.

Nasal swab specimens (one from each nostril) will be obtained at the Randomization Visit and will be cultured by the central microbiology laboratory. Results from the nasal swab specimen cultures will be used to assess correlation with results of the qualifying ETA culture.

Upon determination of eligibility, approximately 354 subjects will be randomized in a 1:1 ratio to 1 of 2 treatment groups:

- ASN100 administered as 2 separate intravenous (IV) infusions of ASN-1 and ASN-2 either sequentially or simultaneously, or
- Placebo administered as 2 separate IV infusions either sequentially or simultaneously.

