5.1.3. Per Protocol (PP) Population

The PP Population includes all subjects in the MITT Population who also meet the following criteria:

- Did not have any major protocol violations that would affect assessment of efficacy,
- Randomized in a timely manner following collection of an ETA specimen showing heavy *S. aureus* colonization;
- Was mechanically ventilated at randomization;
- Had an appropriate chest image performed at randomization;
- Did not have a change of oxygenation and onset of purulent secretions at randomization;
- Was not diagnosed with pneumonia at randomization or within 24 hours of receiving study drug;
- Received an adequate dose of study drug administered in a timely manner following study drug preparation,

- Did not die within 24 hours of receiving study drug,
- Did not have Investigator Diagnosis of Pneumonia within 24 hours of receiving study drug, and
- Complete an adequate number of Monitoring Period assessments through Day 22 based on medical review of available data.

Exclusion from the PP Population will be determined programmatically for each MITT subject. Programmatically determined assignment into the PP Population will be evaluated for confirmation or Sponsor Override as applicable during a Review Meeting.

The final PP Population classification will be performed in a blinded fashion and prior to final database lock and unblinding. After the Review Group's review, any Sponsor Overrides of the PP Population flags will be finalized and documented. The PP Population flags and the reasons for Sponsor Override will also be included in the analysis datasets.

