7.11. Analysis of Efficacy

For all efficacy analyses, subjects will be analyzed in the group to which they were randomized.

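### SAP 7.2 reports subjects given the wrong study drug under their randomized arm in the Per Protocol analysis, and no Per Protocol criterion in SAP 5.1.3 requires the assigned treatment

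*SAP*

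**What the plan says.** SAP 7.2 has two paragraphs. The first covers subjects who were randomized but not treated: they stay in ITT and are left out of MITT, PP, PK and Safety. The second covers subjects who received incorrect study medication. It removes them from no population and says that "they will be reported under their randomized treatment group for all efficacy analyses for the ITT, MITT, and PP Populations"; for safety they go under the treatment received. SAP 7.11 repeats the efficacy rule in general form: "For all efficacy analyses, subjects will be analyzed in the group to which they were randomized".

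PP membership is set in SAP 5.1.3. It starts from MITT and adds ten criteria. The first excludes major protocol violations that bear on the assessment of efficacy; Protocol 10.1 has the same exclusion. The dosing criterion reads "Received an adequate dose of study drug administered in a timely manner following study drug preparation". None of the ten mentions the assigned treatment. Protocol 5.6.5 uses the term study drug for ASN-1, ASN-2 and the matching placebos alike, so the dosing criterion does not supply that requirement.

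PP flags are set by program, then confirmed or overridden by the sponsor at review meetings, and made final while the data are still blinded.

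**The concern.** A PP analysis is meant to show the result in subjects treated as planned. ITT and MITT should keep misallocated subjects under the randomized arm, and nothing here questions that. PP should not carry the same error. If a placebo-randomized subject given ASN100 passes the PP criteria, 7.2 makes that subject a PP placebo subject, and the reverse holds for an ASN100-randomized subject given placebo. If the drug works, this pulls the PP contrast towards zero, so PP could not show the result free of misallocation.

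PP is used widely: for the primary endpoint and its additional analyses (SAP 7.11.2), the secondary and exploratory endpoints (7.11.3 and 7.11.4) and the subgroups (7.12). Each dose is also made up as two separate bags, each pooled from nine vials (Protocol 5.6.3), so an error in one component only is conceivable. Neither 7.2 nor 5.1.3 says how to classify it.

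**Working it through.** **Reading the sections together**

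1. If the major-violation criterion in 5.1.3 covers a wrong-arm dose, these subjects are not in PP, and the mention of PP in 7.2 either has no effect or contradicts 5.1.3.
2. If it does not cover it, the other nine criteria do not catch the error, and the subject is counted in PP under the arm not received.
3. The text does not choose between these. The decision falls to a blinded review, which may not be able to see that the wrong drug was given.

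**The plan's own figures** (SAP 6: two-sided 0.05, 80% power, 25% versus 12.5%)

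With pooled variance under the null and no continuity correction,

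n = [1.960 × √(2 × 0.1875 × 0.8125) + 0.8416 × √(0.25 × 0.75 + 0.125 × 0.875)]² / 0.125² = 151.9, which rounds up to 152.

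This matches "152 evaluable subjects are required in each treatment group"; power at 152 per arm is 80.03%. For non-evaluable subjects, 152 / 0.86 = 176.7, so 177 per arm and 354 in all, which matches "Assuming a 14% non-evaluable rate, approximately 354 subjects (177 subjects per treatment group) will be randomized". None of these figures is in dispute.

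**Size of the dilution (illustrative)**

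The documents give neither a misallocation rate nor an expected PP size. Assume 152 PP subjects per arm, the planned rates, and k subjects in each arm who received the other arm's treatment and carry its event rate.

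- Placebo rate as labelled: 25 × (1 − k/152) + 12.5 × k/152.
- ASN100 rate as labelled: 12.5 × (1 − k/152) + 25 × k/152.
- Difference: 12.5 × (1 − 2k/152), so each swapped pair costs 12.5 × 2/152 = 0.16 points.

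| k per arm | Share of arm | Difference if kept as randomized | Power if kept | Power if excluded (difference 12.5) |
|---|---|---|---|---|
| 0 | 0% | 12.50 | 80.0% | 80.0% |
| 1 | 0.7% | 12.34 | 79.0% | 79.8% |
| 2 | 1.3% | 12.17 | 77.9% | 79.5% |
| 3 | 2.0% | 12.01 | 76.7% | 79.2% |
| 5 | 3.3% | 11.68 | 74.4% | 78.7% |
| 8 | 5.3% | 11.18 | 70.7% | 77.9% |

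If only ASN100-randomized subjects are affected, the difference is 12.5 × (1 − k/152): 12.25 points and 78.2% power at k = 3, and 11.84 points and 75.0% at k = 8.

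**The case against.** A reader might infer that the SAP keeps wrong-drug subjects in PP. The documents do not say so. In 7.2, the paragraph on untreated subjects deals with membership; the paragraph on wrong-drug subjects deals with the arm they are reported under. Membership belongs to 5.1.3. In a single-dose trial, receiving the other arm's treatment can readily be read as a major violation affecting efficacy. The Population and Outcome Plan, which governs the review meetings, is not among the documents and may settle the matter. All of this stands. It does not remove the gap: the SAP names PP in a rule for these subjects, and its own detailed criteria never exclude them by name.

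A reader might also infer a wider fault in PK and immunogenicity. This has little support.

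- **PK:** 7.2 does name the PK Population for untreated subjects and is silent only on wrong-drug subjects. SAP 5.2.5 lists the PK parameters as secondary efficacy endpoints, so 7.11 read literally would group them as randomized. But 5.2.5 defines them as following a dose of ASN100, and SAP 7.11.5 sends PK to a standalone plan, which is not available here.
- **Anti-drug antibodies:** they are a safety endpoint in SAP 5.2.7, so the actual-treatment rule in 7.13 already applies.

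Finally, the effect is hypothetical. Allocation runs through a central system, no misallocation is reported, and PP is not the primary analysis. This limits the importance of the point without answering it.

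**Conclusion.** The point holds as an unresolved inconsistency between SAP 7.2 and 5.1.3. A wrong-drug subject can stay in PP under the arm not received, or can be excluded by blinded judgement, and the plan does not say which. If such subjects stay and the drug works, the PP contrast is diluted: from 12.5 points to 12.2 at two swaps per arm and to 11.7 at five, a loss of about 7% of the difference (10/152).

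These sizes assume 152 PP subjects per arm, the planned event rates, equal swaps in both arms and the full event rate of the treatment received. The effect is small unless misallocation reaches several percent. The primary MITT analysis, where as-randomized reporting is appropriate, is not touched. The correction is worth making because it is cheap and the population rule is pre-specified; the trial's main result does not depend on it.

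**What to change.** - **SAP 7.2:** delete PP from the sentence on incorrect study medication. Leave ITT and MITT as randomized.
- **SAP 5.1.3:** add that receipt of study medication belonging to the other arm, for either component, is a major violation that excludes the subject from PP.
- **Keep the exclusion narrow:** incomplete dosing should stay under the existing adequate-dose criterion. A broader rule, excluding anyone who did not receive both assigned components, would also remove subjects whose second infusion was withheld because of an adverse event under Protocol 5.6.3. Those subjects were not misallocated.
- **Blinding:** PP flags must be final before unblinding, so wrong-drug cases should be flagged without unblinding the Review Group, for example by a party independent of it.
- **PK:** add a cross-reference to the standalone PK plan for grouping by treatment received. No change is needed for anti-drug antibodies.

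The cost is a few sentences, which SAP 3 allows before unblinding, plus an arrangement for the independent flag. Treatment received must be derived for the Safety Population in any case, but that does not make it available to the blinded group, which is why the flag is needed. PP may lose a few subjects: in the illustration, excluding five per arm leaves 147 per arm and 78.7% power, against 74.4% if they are kept as randomized.
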